### 8.2.1. Inclusion Criteria

Patients must meet all of the following inclusion criteria to be eligible for inclusion in the study:

1. Age ≥18 years at prescription/administration of conventional systemic therapy
2. An ICD-10 diagnostic code for AD provided by a dermatologist (Table I)
3. Have filled/administered the same conventional therapy twice (Table II)

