### **Registries utilized in this study:**

The Danish National Patient Registry (DNPR) holds information on inpatient visits (since 1977) and outpatient visits (since 1995), along with data on medical procedures, including hospital-administered biologics and phototherapy. Diagnoses are recorded based on the International Classification of Diseases (ICD-8 from 1977 to 1993 and ICD-10 from 1994 onward). Hospital-administered procedures and treatments are registered using the SKS codes, while surgical procedures have been recorded according to the NOMECCO Classification of Surgical Procedures (NCSP) since 1996.

The Danish Register of Medicinal Product Statistics contains information on all filled prescriptions at community pharmacies from 1995 onwards, using the Anatomical Therapeutic Chemical (ATC) classification system.

The National Cause of Death Registry holds information on the cause and date of death when applicable.

The National Population Registry contains demographic information, including vital status and gender.

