### Treatment series

Treatment series are defined as periods of time in which a patient is considered on active treatment. The allowable gap between administrations of the same drug is 150 days to aggregate the treatment series. If the gap exceeds 150 days, patients are considered to have initiated a new treatment series. The allowable gap is based on the common gap of 90 days between each filled prescription, with an additional extension of 60 days to mirror the design of ORALSURV, which allowed for up to 2 months of discontinuation for safety issues.

The duration of active therapy following the last filled prescription or administration is set at 120 days, reflecting the standard 90-day prescription interval plus an additional 30 days, as outlined by Fleischmann et al. . Each treatment series is considered separately, as concomitant therapies were allowed in the ORALSURV study design.

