To evaluate the robustness of the method applied to handle overlapping events in the primary analysis, multiple sensitivity analyses will be performed, in which overlapping events will alternatively be assigned to (a) the most recently administered drug, (b) attributed to both drugs, or (c) excluded by censoring the patient at the time of the event. These results will be presented separately.

Furthermore, a sensitivity analyses will be conducted reporting incidence rates for the years 1995-2001, 2002-2008, 2009-2015, and 2016-2022.

As a sensitivity analyses, a cox regression model with inverse Probability Treatment Weighting will be conducted.

Analyses will be conducted using SAS 9.4, Python v3.11.5, and R v4.4.1

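### One 120-day tail and one 150-day gap, derived only from 90-day prescriptions, are applied to all five drugs and to hospital administrations, and no listed analysis tests a shorter window

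*Protocol*

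**What the plan says.** Section 8.7 of the protocol (Treatment series) fixes two exposure parameters.

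- **Gap:** "The allowable gap between administrations of the same drug is 150 days to aggregate the treatment series". Its basis: "The allowable gap is based on the common gap of 90 days between each filled prescription, with an additional extension of 60 days". Beyond that, "If the gap exceeds 150 days, patients are considered to have initiated a new treatment series".
- **Tail:** "The duration of active therapy following the last filled prescription or administration is set at 120 days". The only reason given for choosing that length is worded as "reflecting the standard 90-day prescription interval plus an additional 30 days".

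Table II (Section 8.3) lists five exposures: cyclosporine, methotrexate, azathioprine, mycophenolic acid and prednisolone. Each has an ATC code and an SKS code. Section 8.4 explains the second kind: "Hospital-administered procedures and treatments are registered using the SKS codes".

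Criterion 3 in Section 8.2.1 reads "Have filled/administered the same conventional therapy twice (Table II", and Section 8.2 places the index date at the second fill or administration. Exposure time is then accumulated per drug from the series, and events within a series are assigned to that drug (Section 8.7, Follow-up and exposure and censoring; Events). The primary and secondary rates are reported for each conventional treatment separately.

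**The concern.** The window is justified by how often prescriptions are filled in the community. Nothing in the protocol carries that reasoning over to a hospital administration, or to a drug that may be given as a short course. The rule nevertheless covers both without distinction.

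The window determines the denominator and decides which events enter the numerator. If the true supply is short, off-drug time is counted as treated time and the drug-specific rate moves toward the off-drug rate. In a safety study that is the unfavourable direction. The effect also differs between drugs, so the five rates would not be on the same footing. The window further determines which treatments count as overlapping, so the overlap rules inherit any misclassification.

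Criterion 3 adds to this. With no minimum spacing between the two qualifying records, two administrations on consecutive days of one admission are enough for entry, although Section 8.2 says the criterion is meant to select patients who actively fill their prescriptions.

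**Working it through.** **1. The protocol's own figures.** Gap: 90 + 60 = 150 days. Tail: 90 + 30 = 120 days. Both reproduce, and both need a supply of about 90 days behind each record.

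**2. Scope against justification.** Both derivations start from the interval between filled prescriptions. The tail is then applied after a fill or an administration alike. No window is specified by drug, by supplied quantity or by record type.

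**3. Dilution over the tail.** Let L be the true days on drug after an isolated last record. L is not in the protocol and is assumed here. RR is the true on-drug rate ratio, also assumed, with no excess risk once the drug is stopped.

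- Share of the tail on drug = L/120
- Ratio seen over the tail = 1 + (RR − 1) × L/120
- For comparison, a supply-based window using the protocol's own 30-day extension lasts L + 30 days, and the ratio seen is 1 + (RR − 1) × L/(L + 30)

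| L (days) | Share of 120 days on drug | Ratio seen, RR = 2 | Ratio seen, RR = 3 | L + 30 (days) | Ratio seen over L + 30, RR = 2 |
|---|---|---|---|---|---|
| 7 | 5.8% | 1.06 | 1.12 | 37 | 1.19 |
| 14 | 11.7% | 1.12 | 1.23 | 44 | 1.32 |
| 30 | 25% | 1.25 | 1.50 | 60 | 1.50 |
| 60 | 50% | 1.50 | 2.00 | 90 | 1.67 |
| 90 | 75% | 1.75 | 2.50 | 120 | 1.75 |

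The fixed tail agrees with its own derivation only at L = 90.

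**4. Person-time.** Section 8.2 expects around 1,000 patients for most treatments. If each contributed one isolated window, 1,000 × 120/365.25 = 329 person-years would be credited. The time truly on drug would be 19, 38 or 82 person-years for L = 7, 14 or 30.

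**5. Joining of courses.** If the index record is followed by one more record 150 days later, the series runs 150 + 120 = 270 days from index. With two 7-day courses, 14/270 = 5% of it is on drug. If the two records are instead the qualifying pair, follow-up starts at the second and only 120 days count.

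**6. Check on regular users.** Take eight fills 90 days apart, each a 90-day supply (assumed). Follow-up from the second fill is 6 × 90 + 120 = 660 days. Supply over that time is 7 × 90 = 630 days. The excess is 30/660 = 4.5%, and a true ratio of 2 would appear as 1 + 630/660 = 1.95.

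**7. Do the planned extra analyses test the window?** Section 8.7 says "To evaluate the robustness of the method applied to handle overlapping events in the primary analysis, multiple sensitivity analyses will be performed". Those analyses reassign or censor overlapping events. The others vary the number of uses needed for entry, the calendar period and the weighting. None changes 120 or 150 days. One-use entry admits single records outright. The intention-to-treat analysis drops the series but assigns later events to the index treatment, so it only lengthens the window. Section 8.9 mentions adherence and other indications, but not window length.

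**The case against.** The case for leaving the rule alone has several parts.

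- **Two records are required.** A reader might infer that one in-hospital dose alone brings a patient into the main analysis with 120 days of exposure. It does not: entry needs two records of the same drug and follow-up starts at the second. A reader might also infer that two short courses four months apart always yield about 240 days of counted exposure. When they are the qualifying pair, only about 120 days count. Both points stand. What remains is that the two records may fall within one hospital contact, and that the last record always receives the full tail.
- **The meaning of an SKS record is not stated.** Section 8.4 says only that hospital-administered treatment is registered with these codes. A record could be one dose, the start of a course or medicine supplied by a clinic. That stands: one record as one dose is an assumption. The protocol's 90-day reasoning is equally unsupported for these records.
- **The ratios describe isolated records.** The tail is added once, and regular users show an excess of 4.5%. That stands. The protocol gives neither the share of isolated short users nor the split between hospital records and community fills. The inference that most prednisolone person-time is off drug therefore has no support.
- **A longer risk window can be deliberate.** The primary endpoint is MACE and malignancy, and the added 30 and 60 days are linked to two cited safety studies. For malignancy a longer window may well be defensible. Serious infection, herpes zoster and venous thromboembolism, where the no-carry-over assumption is more natural, are secondary.
- **A sensitivity analysis could sit in a statistical analysis plan.** It could, but the point here is a stated rule whose justification does not cover its stated scope.

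**Conclusion.** The point holds in a limited form. The 120-day tail and 150-day gap are justified only for community prescriptions filled about every 90 days, yet they apply to all five drugs and to hospital administrations. No listed analysis shortens the window. Two administrations in one hospital contact can meet criterion 3 and open 120 days of exposure.

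For isolated records with a true duration of 7 to 60 days, a true ratio of 2 would appear as 1.06 to 1.50 over the tail, and a true ratio of 3 as 1.12 to 2.00. These figures rest on assumed durations, assumed ratios and no carry-over risk. They bear mainly on prednisolone and hospital-coded exposure, and on acute outcomes. They do not measure the bias in any drug's overall rate, because the protocol does not show how common isolated short use is. The matter merits a change before analysis, but it does not invalidate the design.

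**What to change.** 1. Keep 150/120 days as the main definition for community fills.
2. For criterion 3, count all SKS records within one hospital contact as a single use.
3. Add a named sensitivity analysis that repeats the prednisolone rates and the SKS-based rates with a shorter window, shown beside the main result. One workable form is supplied quantity plus the protocol's own 30-day extension. Where quantity is unavailable, a 30-day tail with a 60-day gap would serve.

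The 30- and 60-day fallback values are a convention, not derived from the protocol. They reduce the dilution without removing it: a 7-day course with a true ratio of 2 would show 1 + 7/30 = 1.23 over a 30-day tail, against 1.06 over 120 days. The shorter window therefore belongs in a sensitivity analysis. It should not replace the main window for hospital records, because true exposure would be lost if those records reflect longer supply.

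The cost is a record-type and drug-specific parameter in the exposure programming and one extra table, with no new data. Those exposures will have fewer person-years and wider intervals.

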### Follow-up and exposure and censoring

Patients are followed from the index date until the earliest occurrence of one of the following: the event of interest, the study closing date (30 December 2022), initiation of a

biological therapy or JAK inhibitor, death, the development of a condition that would qualify for one of the treatments of interest (Table 1), or migration.

When using treatment series, exposure time is calculated and cumulated based on the specific therapy received. Except for the event of interest, any of the previously mentioned cases will result in censoring.

Additional analyses will be conducted on an intention-to-treat basis.

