**TERTIARY OBJECTIVE**

The tertiary objective is to compare the above identified incident rates of adverse events per individual conventional systemic treatment in a dermatologist-verified adult atopic dermatitis

(AD) patient population with the following two matched cohorts: The Danish background population AND Patients diagnosed with AD not receiving systemic therapies (see section 9.7).

**Study Design:** This is a retrospective observational cohort register study.

**Population:** Patients with AD verified by a dermatologist and a background population

**Variables:** Variables include diagnosis for AD (and relevant diagnosis to be excluded), treatment for AD, i.e. conventional systemic therapies (exposures) and advanced therapies (exclusion criteria), outcomes, i.e. adverse events of special interest, including MACE, malignancies (excluding and including non-melanoma skin cancer), serious infections, venous thromboembolism (deep vein thrombosis and pulmonary embolism), dyslipidemia, and herpes zoster, and medical history (key covariates), i.e. alcohol abuse, cardiovascular disease (including heart failure and coronary heart disease), diabetes, dyslipidemia, prior cancer, hypertension, and smoking status.

**Data source:** The Danish National Registries including the Danish National Patient Registry, the Danish Register of Medicinal Product Statistics, the National Cause of Death Registry, and the National Population Registry.

**Study size:** All patients meeting the inclusion criteria will be included for the current data analysis. Since this is a descriptive, retrospective study, no sample-size calculation is performed.

**Data analysis:** Descriptive statistics will summarize patient characteristics using frequencies for categorical variables and means with standard deviations or medians with interquartile ranges for continuous variables.

Incidence rates of outcomes will be reported per 10,000 person-years with 95% confidence intervals.

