### 8.2.2. Exclusion Criteria

Patients meeting any of the following criteria will not be included in the study:

1. Current or previous cancer prior to inclusion (except NMSC) (Table III)
2. History of biological therapy prior to inclusion (Table II)
3. History of JAK inhibitor prior to inclusion (Table II)
4. History of prespecified diseases that could be treated with the conventional drugs of interest i.e., RA, IBD, PsA, and PsO (Table I)

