**Systemic treatment for AD and other indications (biological therapy and targeted synthetic DMARDs)**

Variable (Exclusion criteria)	Role	Data Source	Operational Definition (ATC Code)	Operational Definition (SKS Code)
Baricitinib	Treatment, exclusion criteria	Registry of Medicinal Products Statistics	L04AF02	BWHP106
Upadacitinib	Treatment, exclusion criteria	Registry of Medicinal Products Statistics	L04AF03	BWHP107
Dupilumab	Treatment, exclusion criteria	Registry of Medicinal Products Statistics	D11AH05	BOHJ18B8

Table III. Outcomes.

Variable (ICD-10 diagnostic code description)	Role	Data Source	Operational Definition (ICD-8 diagnostic code)	Operational Definition (ICD-10 diagnostic code)
Dyslipidemia	AE, sec. outcome	National Patient registry		E78 (pre-defined macro)
Herpes zoster 			053.00–053.9	B02
		MACE 		
Stroke	AE, part of primary outcome (MACE)	National Patient registry	NA	I61, I63, I64
Myocardial Infarction	AE, part of primary	National Patient registry	NA	I21, I22

090177e1a4d83c92Approved\Approved On: 11-Nov-2025 17:27 (GMT)

	outcome (MACE)			
CV death (cause of death) 	AE, part of primary outcome (MACE)	National Patient registry	NA	Cause of Death: ICD10: I20-25, I60-61, I63-64, I69, G45.8-45.9, I71, I74, I11.0, I13.0, I13.2, I50, Z95, I46.1, I65, I66, I67.0, I67.2, I70.
Malignancies				
Malignancies, excluding NMSC	AE, co-primary outcome (Malignancy)	National Patient registry	140-209 (except 173)	C00-C99, expect C44
NMSC	Exclusion criteria	National Patient registry	173	C44
Serious infections 	AE, sec. outcome	National Patient registry	Table V	Table V
Arterial thromboembolisms (AT) Venous thromboembolism Deep vein thrombosis (DVT) and pulmonary embolism (PE) 	AE, sec. outcomes	National Patient registry	DVT: 451 PE: 450.99 AT: 444	DVT: I801, I80.2, I80.3, I80.8, I80.9, I82.2, I82.3, I82.9 PE: I26 AT: I74 And anticoagulation therapy: ATC B01A

Table IV. ICD-8 and ICD-10 for medical history

Variable (ICD-10 diagnostic code description)	Role	Data Source	Operational Definition (ICD-8 diagnostic code)	Operational Definition (ICD-10 diagnostic code)	Operational Definition (Nordic Medico-Statistical Committee (NOMESCO) Classification of Surgical Procedures codes)
Alcohol abuse	medical history	National Patient registry	291, 303	F10.1–10.9 (pre-defined macro)	NA
Heart failure	medical history	National Patient registry	NA	I11.0, I13.0, I42, I50	NA

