CVD Risk Factors					

090177e1a4d83c92ApprovedApproved On: 11-Nov-2025 17:27 (GMT)

History of coronary heart disease 	medical history	National Patient registry	NA	I20-I25	PCI (KFNG00, KFNG02, KFNG02A, KFNG05, KFNG05A, KFNG10, KFNG12, KFNG20, KFNG22, KFNG30, KFNG40, KFNG96, KZFX01) or CABG (KFNA, KFNB, KFNC, KFND, KFNE, KFNF, KFNH, KFNJ, KFNK, KFNW)
Diabetes	medical history	National Patient registry	250	E10-E14 (pre-defined macro)	NA
Dyslipidemia (within the past 5 years)	medical history	National Patient registry	NA	E78 (pre-defined macro)	NA
History of cancer	medical history	National Patient registry	140-209	C00-C96	NA
Hypertension	medical history	National Patient registry	400-404 (pre-defined macro)	I10.x-I15.x (pre-defined macro)	NA
Smoking history	medical history	National Patient registry	NA	Pre-defined macro	NA

Table V. ICD-10 Serious infection (see table III, role for all: AE and Secondary Outcome; Data Source: National Patient Registry)

Serious infections	Operational Definition: ICD-10
CNS infections	A02.21, A06.6, A17.0, A20.3, A27.81, A32.1, A39.0, A80-A89, B00.3, B00.4, B01.0, B01.1, B02.0-B02.2, B05.0, B05.1, B06.0, B26.1, B26.2, B10.01, B37.5, B38.4, B43.1, B45.1, B46.1, B58.29, G00-G08

090177e1a4d83c92\Approved\Approved On: 11-Nov-2025 17:27 (GMT)

Gastrointestinal infections	A00, A01, A02.0, A02.8, A02.9, A03-A05, A06.0, A06.2-A06.4, A07-A09, A21.3, A22.2, A42.1, B05.4, B15-B19, B25.1, B46.2, K35, K37, K57, K61, K62.0, K65.0, K65.9, K67, K75.0, K81.0, K81.8, K81.9
Gynecological infections	N70.0, N70.9, N71.0, N71.9, N72, N73.0, N73.2, N73.3, N75.5, N73.8, N73.9, N74
Heart infections	A32.8, B33.21, B37.6, I00, I01, I30, I32, I33, I38-I41, I43.0
Hepatitis	B16, B17, B18
HIV	B20-B24
Musculoskeletal infections	A02.23, H05.029, M00-M03, M46.2, M46.3, M46.5, M46.6, M60.0, M65.0, M65.1, M71.0, M71.1, M86.0-M86.2, M86.8, M86.9, M90.0, M90.1, M90.2
Opportunistic infections	A02, A07.2, A07.3, A15-A19, A27.0, A31, A32, A40.3, A42-A44, A48.1, A48.1, A60.0, A81.2, B00-B02, B17.9, B25, B27.1, B37-B40, B44, B45, B55, B58, B59, B78, B95.3, G02.0, G02.1, J13, J17.1, J17.2, K23.0, K67.3, K93.0
Pulmonary infections	A48.1, A37, B39-B40, B01.2, B05.2, B25.0, B44, B58.3, B59, B95.3, J10-J22, J85, J86, U04
Sepsis	A02.1, A20.7, A22.7, A24.1, A26.7, A28.2B, A32.7, A40, A41, A42.7, B37.7, R65.0, R65.1, R65.9

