## Events

During the treatment series, an adverse event can be adjudicated to the ongoing treatment. In the intention-to-treatment (ITT) study design, the event can be adjudicated to the treatment initiated at the index date.

If a patient is receiving overlapping treatments, any adverse event occurring during both therapies will be adjudicated to the therapy the patient has been on for the longest duration. Such events are referred to as overlapping events.

In the primary analyses, for overlapping events, the event is assigned to the drug the patient has been on the longest.

Multiple sensitivity analyses will be conducted to address overlapping events:

- The event is assigned to the most recent drug.
- The event is attributed to both drugs.
- The event is attributed to neither drug and the patient is censored.

Serious infections are defined as those requiring hospital admission for more than one day (Table V), and infections with HIV, hepatitis B or C, tuberculosis, or infections resulting in death.

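### For dyslipidemia, NMSC, HIV, hepatitis B/C and tuberculosis, the protocol does not remove patients who already have the condition, so re-coded prevalent disease may be counted as incident

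*Protocol*

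**What the plan says.** **Follow-up.** Protocol Section 8.7, in its part on follow-up and censoring, gives this rule: "Patients are followed from the index date until the earliest occurrence of one of the following: the event of interest". Further end points of follow-up are study close, start of a biologic or JAK inhibitor, death, a qualifying disease and migration. History of the outcome is not mentioned.

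**Eligibility.** Section 8.2.2 excludes "Current or previous cancer prior to inclusion (except NMSC) (Table III", prior biologic or JAK inhibitor use, and "History of prespecified diseases that could be treated with the conventional drugs of interest i.e., RA, IBD, PsA, and PsO (Table I". Of these, only cancer is a study outcome.

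**Dyslipidemia.** In Table III it is a secondary outcome under E78. In Table IV it is medical history under the same E78: "Dyslipidemia (within the past 5 years". The abstract lists the history variables as "medical history (key covariates), i.e. alcohol abuse, cardiovascular disease (including heart failure and coronary heart disease), diabetes, dyslipidemia, prior cancer, hypertension, and smoking status".

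**NMSC.** It is a secondary endpoint (Section 8.1) and is exempt from the cancer exclusion (Section 8.2.2). Its row in Table III reads "NMSC Exclusion criteria National Patient registry".

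**Serious infections.** Section 8.7 (Events) asks for an admission of more than one day, and then adds "infections with HIV, hepatitis B or C, tuberculosis, or infections resulting in death".

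**Denominator.** Section 8.7 reports rates per 10,000 person-years at risk but does not define being at risk for each outcome.

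**The concern.** An incidence rate needs a numerator of new cases and a denominator of people who could become one. Dyslipidemia, HIV, chronic hepatitis and NMSC can be coded again at later contacts, long after diagnosis. If patients with such a condition enter the cohort and the first code after index ends their follow-up, the recorded event may be old disease.

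The protocol accepts the principle for one outcome: Section 8.2 explains that prior cancer is excluded so that observed events are not due to earlier disease. It does not take the same step for the chronic secondary outcomes. Section 10 says that individual patient data are not retrieved or validated, so nothing later in the process would separate a re-coded case from a new one. At stake are the absolute rates of these outcomes, which the secondary objective is meant to deliver.

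**Working it through.** **1. The rules applied to a patient who already has the condition**

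| Outcome | Excluded at entry? | First code after index |
|---|---|---|
| Malignancy other than NMSC | Yes (8.2.2) | New disease |
| Dyslipidemia (E78) | No; kept as history and covariate (Table IV, abstract) | Ends follow-up as an event, new or old |
| NMSC (C44) | Unclear: exempt in 8.2.2, exclusion criterion in Table III | Depends on which text is followed |
| HIV, hepatitis B/C, tuberculosis | No rule | Qualifies; no new-onset requirement and, on the natural reading, no admission requirement (8.7, Events) |

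Table V includes B18 and B20-B24. Section 8.4 says that the patient registry has held outpatient visits since 1995. A follow-up visit for known HIV or chronic hepatitis could therefore qualify.

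**2. The protocol's own figures**

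The protocol gives no prevalence, re-coding frequency or expected rate for any of these outcomes. The one event rate it uses to support its size is MACE at 1.5% a year in 13,000 patients: 13,000 × 0.015 = 195, consistent with its statement of over 100 events a year. That figure has no bearing on this point.

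**3. Illustration with assumed inputs**

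Let p be the share with prevalent disease at index, r the yearly hazard that such a patient is coded again, and λ the true yearly hazard in everyone else. Each patient is followed for one year or until the first code.

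- Events per patient = (1 − p)(1 − e^−λ) + p(1 − e^−r)
- Person-years per patient = (1 − p)(1 − e^−λ)/λ + p(1 − e^−r)/r
- Apparent rate = events / person-years

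Example with λ = 0.01, p = 0.02, r = 0.1:

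- Events: 0.98 × 0.00995 + 0.02 × 0.09516 = 0.01165
- Person-years: 0.97512 + 0.01903 = 0.99415
- Rate: 0.01165 / 0.99415 = 0.01172, or 117 per 10,000 person-years

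| True rate per 10,000 PY | p | Apparent rate, r = 0.1 | r = 0.3 | r = 0.5 |
|---|---|---|---|---|
| 50 | 2% | 68 | 101 | 128 |
| 50 | 5% | 95 | 179 | 247 |
| 50 | 10% | 141 | 309 | 449 |
| 100 | 2% | 117 | 151 | 178 |
| 100 | 5% | 143 | 227 | 296 |
| 100 | 10% | 187 | 355 | 496 |

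The multiples are 1.2 to 5.0 for a true rate of 100 and 1.4 to 9.0 for a true rate of 50. Removing the prevalent patients (p = 0) returns the true rate. The upward direction needs only r > λ. The excess shrinks with longer follow-up, because prevalent patients leave at their first code.

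**The case against.** **Silence is not a statement.** No sentence says that prevalent cases are counted, and the terms incidence and person-years at risk point the other way. At-risk sets and look-back windows are often left to a statistical analysis plan. This stands as far as wording goes: the accurate claim is that such cases may be counted. It does not remove the point, because the protocol itself fixes eligibility, outcome codes and follow-up, gives E78 two roles, and gives NMSC contradictory ones.

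**Table III hints at look-back.** It lists ICD-8 codes for zoster, DVT, PE, arterial thromboembolism and NMSC. ICD-8 was in use only until 1993 and the study starts in 1995, so those codes could serve only to find earlier disease. That is a fair inference but not a rule, and of the outcomes at issue here it helps only NMSC. The ICD-8 entry for dyslipidemia is empty in Table III and not applicable in Table IV, and Table V gives only ICD-10 codes.

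**Stronger readings that the document does not support.** A reader might extend the point in four ways:

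- *To prior vascular disease.* Table IV does keep "History of coronary heart disease" as history. But a new MI, stroke or VTE after earlier disease is a real event, and first-ever versus new episode is a design choice. The history range I20-I25 is also mostly outside the non-fatal MACE codes.
- *To every secondary rate.* Death cannot be prevalent, and most serious infections need an admission of more than one day.
- *To re-coding that is heavier in treated patients.* This is plausible, but the protocol gives no contact frequency by group, and the untreated AD comparator is also hospital-diagnosed. Matching may also use cardiovascular risk factors, among which Table IV lists dyslipidemia.
- *To a large stated inflation.* Assuming 5% to 20% prevalence, 30% to 60% re-coded in year 1 and 1% true incidence gives 0.05 × 0.3 + 0.95 × 0.01 = 2.45% up to 0.20 × 0.6 + 0.80 × 0.01 = 12.8%, about 2.5 to 13 times. Every input is assumed, so this shows only how much the answer depends on them.

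**Conclusion.** The point holds for dyslipidemia, NMSC, and HIV, hepatitis B/C and tuberculosis within serious infections. As written, the rules allow a re-coded chronic condition to end follow-up as an incident event, and the absolute rates of these outcomes may be too high. For NMSC the finding is a contradiction between Sections 8.1 and 8.2.2 and Table III, which would lead two analysts to different cohorts.

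The size is unknown. The illustrative 1.2 to 5.0 times (true rate 100 per 10,000 person-years, one year) rests on assumed prevalence and re-coding and is no estimate for this study. What happens to the hazard ratios depends on prevalence and re-coding in each group and on how they differ between groups; the protocol states none of this, so no direction can be claimed. The primary malignancy outcome is already protected by the exclusion of prior cancer, and MACE is outside this point. The change should be made, but it does not threaten the primary objective.

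**What to change.** - For dyslipidemia, NMSC, HIV, hepatitis B/C and tuberculosis, exclude from that outcome's analysis anyone with a qualifying code before index. For the three infections, apply this to the component, so that such a patient stays at risk for other serious infections.
- Apply the same rule to the treated cohort and both matched comparators.
- State the look-back. The 5-year window for dyslipidemia as a covariate need not serve here: a patient whose only code is older would pass a 5-year filter.
- Note the limit on look-back. Outpatient records start in 1995, the year the study period opens, and the last index date is 31 December 2021. Outpatient look-back therefore runs from almost nothing to nearly 27 years, and some prevalent disease in early entrants will remain. The planned rates by calendar period are a natural place to show this.
- Reconcile NMSC across Section 8.1, Section 8.2.2 and Table III.

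The cost is a few sentences, a filter on registries that are already linked, and slightly fewer patients per outcome.
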